This study is powered to detect a clinically significant difference between iCBT and the usual care conditions. Meta-analysis of medical and behavioral outcomes indicates that a medium effect-size between conditions will have a significant impact on quality of life. In a previous study we observed an average effect of about $d=0.55$ SD. To allow for a somewhat smaller effect in this proposed study, we design our study to have 80% power to detect clinically significant effect of $d=0.5$ SD. In the pilot data, we found a within-subject correlation structure consistent with a stationary autoregressive process with correlation parameter 0.4. We also assume a dropout rate of 20% for these power calculations. With these assumptions on effect size, covariance structure, and dropout rates, and with a two-sided alpha level of 0.05, the methods of Hedeker et al.⁸⁶ estimate that a sample size of 48 subjects per group will provide 80% power for the test of our primary hypothesis.

We believe that this is a conservative estimate, based on the larger effect size observed in our prior study, and the higher than expected dropout rate used in the calculation. In addition, our analyses will use the baseline measure of Psychosocial Functioning as a covariate, which should reduce the standard errors in our test, and therefore increase the smallest detectable effect size.

4.2. Define plans for data and statistical analysis, including key elements of the statistical plan, stopping rules and endpoints.

Planned Analyses

(i) Overview

Logistic, log-linear and linear random effects models (hierarchical regression models) will be implemented with random intercepts and slopes for longitudinal binary, count, and continuous outcomes, respectively. These models will contain separate main effects for change from baseline to each follow-up visit at 6, 12, and 18 months, main effect for the treatment, and interactions between the visit and treatment indicator variables. For each of the primary (workforce participation indices) and the secondary (Work Behavior Inventory, Specific Levels of Function) outcomes, separate intent-to-treat (ITT) tests and estimates (with 95% confidence intervals) of randomized group contrasts at 6, 12, and 18 months will be obtained from the estimates of the respective time-treatment interactions.

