While the present study is designed to minimize lost observations, the proposed random effects or hierarchical regression approach is superior to last observation carried forward in minimizing bias and Type 1 error and inferentially equivalent to multiple imputation.⁷⁹ To assess the sensitivity of treatment effect estimates to missing data, we will compare the results under the above hierarchical regression models with those based on shared parameter models that account for informative missingness that is dependent on unobserved outcomes through a latent variable.⁸⁰ If the results between the two approaches are similar then we will present the proposed hierarchical regression models as robust to informative missing data; otherwise we will note that the results may be

sensitive to informative missing data and augment them with those based on the shared parameter model.

(ii) **Work outcome.** The primary trial outcome measure, workforce participation (composite index) at 6, 12 and 18 months analyzed in the manner described above. A significant ITT difference on the total WBI score across 6 and 12 months would support the hypothesis that iCBT is more efficacious than usual care at improving work outcomes by the end of treatment (Primary Aim 1). Similarly, WBI score at 18 months is a secondary outcome, and a separate ITT effect on work outcomes at 18 months with the respective month-treatment interaction in favor of iCBT would support the hypothesis that it promotes better work outcomes than usual care during the 6 months after the completion of treatment (Secondary Aim 2).

(iii) **Functional outcome.** The second trial outcome measures include the Work Behavior Inventory and the total score on the Specific Levels of Functioning Inventory (SLOF) at 12 months A significant ITT difference on the WBI and the total SLOF score across 6, 12 months would support the hypothesis that ICBT is more efficacious than usual care at improving functioning by the end of treatment (Secondary Aim 1). Similarly, WBI and SLOF total score at 18 months is a secondary outcome, and the separate ITT effects on functioning at 18 months with the respective month-treatment interaction in favor of iCBT would support the hypothesis that it promotes better functioning than usual care during the 6 months after the completion of treatment (Secondary Aim 3).

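### Read in the ordinary way, the random-intercept-and-slope model does not reproduce the AR(1) correlation behind the sample size, and the 12-month standard error comes out modestly too small

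*Combined protocol and SAP*

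**What the plan says.** Section W, item 4.1 (Power analysis) states that in the pilot data "we found a within-subject correlation structure consistent with a stationary autoregressive process with correlation parameter 0.4". The sample size of 48 per group rests on this, together with "80% power to detect clinically significant effect of $d=0.5$ SD", a two-sided alpha of 0.05 and 20% dropout.

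Item 4.2 (i) Overview specifies logistic, log-linear and linear models that "will be implemented with random intercepts and slopes for longitudinal binary, count, and continuous outcomes". The mean model has "separate main effects for change from baseline to each follow-up visit at 6, 12, and 18 months, main effect for the treatment", plus visit-by-treatment interactions, and "randomized group contrasts at 6, 12, and 18 months will be obtained from the estimates of the respective time-treatment interactions". Item 4.2 (ii) words Primary Aim 1 as a difference "across 6 and 12 months would support the hypothesis that iCBT is more efficacious than usual care at improving work outcomes"; item 4.2 (iii) words Secondary Aim 1 in the same way.

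The plan does not give the residual covariance, whether intercept and slope are correlated, the lag to which 0.4 applies, or any robust standard error. The planned model checks cover skewness and kurtosis of residuals and informative missing data. None looks at the covariance structure.

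**The concern.** A stationary AR(1) process has constant variance and correlations that fall geometrically: 0.4, 0.16 and 0.064 over one, two and three visits, if 0.4 applies per visit. Random intercepts and slopes with independent residuals make the variance a quadratic function of time and each covariance a product form in the two visit times. The two shapes do not coincide.

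Visit is categorical in the mean model, so the estimated treatment effects are unbiased with complete data. What suffers is the standard error, and with it the confidence interval and p-value at each visit. This is misspecification, so a larger sample would not remove it, and alpha is set at an uncorrected 0.05. Twelve months is the end of treatment, and it also enters the 6-and-12-month contrast.

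**Working it through.** **1. The plan's own figure.** Inputs from item 4.1: d = 0.5, AR(1) 0.4, two-sided alpha 0.05, 80% power, 20% dropout. Assume that dropout builds evenly to 18 months, so retention is r6 = 1 − 0.2/3 = 0.933 and r12 = 1 − 0.4/3 = 0.867. For the mean of 6 and 12 months, without baseline adjustment:

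- v = ¼ [1/r6 + 1/r12 + 2(0.4)/√(r6·r12)] = 0.779
- n = 2(1.960 + 0.842)² × 0.779 / 0.25 = 48.9 per group, against 48 stated; power at 48 is 79.3%

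So 0.4 per visit fits the stated size. With 0.16 in place of 0.4 in the same formula, v = 0.645 and n = 2(1.960 + 0.842)² × 0.645 / 0.25 ≈ 40.5. This supports the per-visit reading but does not prove it, because the plan does not name the contrast it was sized for.

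**2. Best-fitting version of the planned model.** Let S be the AR(1) 0.4 matrix at baseline, 6, 12 and 18 months, and V = ZGZ′ + σ²I, where Z holds the intercept and linear time. The large-sample likelihood fit minimises log|V| + tr(V⁻¹S). With G unrestricted (intercept and slope correlated):

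- variances 1.093, 0.907, 0.907, 1.093 (assumed: 1 throughout)
- adjacent-visit covariances 0.373, 0.280, 0.373 (assumed: 0.4)
- two visits apart 0.233 (assumed: 0.16); three visits apart 0.093 (assumed: 0.064)

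**3. Effect on standard errors.** With complete data and a saturated mean, the estimate is a difference in cell means, so model SE / true SE = √(c′Vc / c′Sc). For change from baseline, c′Vc is 1.255, 1.534 and 2.000 at 6, 12 and 18 months, against c′Sc of 1.200, 1.680 and 1.872. At 12 months the ratio is √(1.534/1.680) = 0.956. Type I error is 2[1 − Φ(1.96 × ratio)].

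| Contrast | G correlated: ratio (type I) | G uncorrelated: ratio (type I) |
|---|---|---|
| 6 months | 1.023 (4.5%) | 1.073 (3.5%) |
| 12 months | 0.956 (6.1%) | 0.934 (6.7%) |
| 18 months | 1.034 (4.3%) | 0.925 (7.0%) |
| Mean of 6 and 12 | 0.974 (5.6%) | 0.972 (5.7%) |

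At 48 per arm with complete data and correlated G, the 12-month SE is 0.2528 SD by the model and 0.2646 SD in truth.

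**4. Sensitivity at 12 months.**

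- Per-visit correlation 0.3 to 0.5, correlated G: SE 3.9% to 4.8% too small.
- Per-visit correlation 0.16 (0.4 applying per 3 months): 2.5% too small (correlated) to 3.3% (uncorrelated).
- Baseline as a covariate with only the three follow-ups modelled, correlated G: ratios 1.042, 0.933 and 1.027 at 6, 12 and 18 months.

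**5. Simulation, 48 per arm.** Complete data, 4,000 trials: type I error 4.7%, 6.4% and 4.6% at 6, 12 and 18 months under the planned model, against 5.5%, 5.3% and 5.5% with unstructured covariance (Monte Carlo SE about 0.3 percentage points). With 20% dropout, 700 trials: SE ratios 1.04, 0.93 and 1.04 under the planned model (Monte Carlo error about 0.03).

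**The case against.** The strongest reply is that the plan never says the residuals are independent. Random intercepts and slopes with an AR(1) residual contain the assumed covariance exactly, and every ratio above becomes 1.00. A reader might infer that the model class as such cannot reproduce the pilot correlation. The documents do not support that: the incompatibility arises on the ordinary reading, in which a model described only by its random effects has independent residuals.

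A reader might also infer that the direction of error is known at every visit. It is not. At 18 months the SE is 3% too large or 7.5% too small, depending on a random-effects covariance that the plan leaves open.

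A third tempting inference is that the main efficacy claims rest on the 12-month figure. Item 4.2 words the end-of-treatment aims across 6 and 12 months, where the error is about 3%.

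Finally, the plan does not say which pilot outcome showed the AR(1) pattern. The WBI is set to 0 while a participant is not working (section O, item 2.1.1), so its variance at baseline may be far below that later on. As an illustration, assume a baseline SD of 0.1 to 0.5 and a 6-month SD of 0.8, relative to the 12- and 18-month SD. With correlated random effects the 12-month ratio is then 1.01 to 1.03, so the anti-conservatism disappears, while the 6-month ratio is 1.20 to 1.30. Anti-conservatism at 12 months is therefore not established for the WBI. The illustration does not vindicate the planned covariance, which still fits poorly.

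**Conclusion.** The concern holds in a limited form. Under the covariance the plan itself uses for sizing, and with independent residuals, the planned linear model understates the 12-month standard error by about 4% to 7%, and by 2.5% to 3.3% if the per-visit correlation is only 0.16. The 12-month direction is the same for per-visit correlations from 0.16 to 0.64, with intercept and slope correlated or not. The 6-and-12-month average is about 3% too small. The 6-month standard error is 2% to 7% too large, and the 18-month direction is undetermined.

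In practice a nominal 5% test runs at about 6.1% to 6.7% at 12 months and about 5.6% for the aim-level contrast. That is modest and would matter only for a borderline result. The figures cover the linear models for continuous outcomes, not the logistic or log-linear ones. They rest on three assumptions: independent residuals, 0.4 per 6-month visit except where varied, and a pilot structure that carries over to the trial outcomes.

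**What to change.** For continuous outcomes, pre-specify before unblinding an unstructured within-person covariance over baseline, 6, 12 and 18 months, with Kenward-Roger degrees of freedom. If it does not converge, fall back to AR(1) with empirical standard errors. The unstructured matrix has 4 × 5 / 2 = 10 parameters, which 96 participants can support. It contains the AR(1) sizing assumption as a special case and also allows a variance that differs by visit, which is the likely situation for the WBI.

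An acceptable alternative is to keep the random intercepts and slopes and add an AR(1) residual or robust standard errors, stating whether intercept and slope are correlated. Either way, item 4.1 should give the lag to which 0.4 applies and the pilot outcome it came from.

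No data or participants are needed. The cost is six covariance parameters more than correlated random effects with one residual variance (10 against 4), and matching wording in item 4.2 (i), where the gamma model and the shared-parameter model are each compared with the hierarchical model.

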Beck Cognitive Insight Scale (BCIS).⁶⁷ The BCIS is a 15-item measure of two components (factors) of cognitive insight—the capacity and willingness to observe one’s experiences and consider alternative explanations (self-reflectiveness) and the overconfidence in the validity of one’s beliefs (self-certainty). Sample items include, “There is often more than one possible explanation for why people act the way they do” and “My interpretations of my experiences are definitely right.” In the original study with inpatients of varying diagnoses, the BCIS showed adequate convergent and discriminant validity and internal consistency ($\alpha = .60-.68$). The original psychometrics and factor structure have now been replicated several times.⁶⁹ Taken together, the research on the BCIS suggest that cognitive insight has important clinical significance for people with schizophrenia, that it may be a mediating variable in cognitive therapy for the disorder, and that it should therefore be assessed and addressed in clinical trials.⁶⁹

Collection of information from the Work Behavior Inventory (WBI).⁵⁵ The WBI is a 35-item scale specifically designed to assess the work behaviors of individuals suffering from severe mental illness. The WBI is completed as a routine standard of care measure during Supported Employment procedures. As part of usual care, the SE Specialists observes the patient in his/her work setting and also speak to the subject’s supervisor (when the veteran allows this). As part of the research study, we will collect information from the WBI at the time of the baseline and follow-up assessments. The measure will have a value of ‘0’ at points in which the participants are not working. WBI data may be missing if research participants refuse to allow the SE specialist to observe at the worksite and/or speak to employers. Data from the WBI will be analyzed along with other research data whenever available. The WBI is broken down into specific areas, including social skills, cooperativeness, work habits, work quality, and personal presentation. Each item is scored on a 5-point scale, with higher totals indicating stronger work performance. The WBI has been found to have good validity and reliability⁵⁵ and predicts vocational outcomes and productive activity after discharge from rehabilitation.

Performance measures

a) Cognitive

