To ensure the safety of participants, review of all collected information in the form of surveys and interview data will be conducted by study staff. If any current evidence of major depression, suicidal ideation, or homicidal ideation with no intent is present, this information will be discussed with the participant by a psychiatrist or doctoral level psychologist. The information will be provided to their mental health care provider for follow-up. In the case that a subject does not have a mental health care provider (e.g., they have left care against advice and/or after enrollment in the research study) they will be referred appropriately for treatment. If indicated, assistance will be provided in making this contact. If suicidal ideation or homicidal ideation with intent is present or there are reports of abuse of a child or elder, the participant will be referred for evaluation in the nearest emergency room and the treating mental health care provider will be notified. In emergent situations, emergency assistance will be sought from hospital security and/or by contacting 911 emergency services. Subjects may be withdrawn from the study if they are considered a risk to themselves or others. Subjects may continue with the study if they are psychologically stable, even if they do not have a current treating psychiatrist. However, they will be encouraged to reestablish clinical care.

4. Statistical Analysis

- 4.1. Include statistical power calculations and the assumptions made in making these calculations.

Power analysis

For the primary outcome variable (composite index of workforce participation), and secondary outcome, Work Behavior Inventory (WBI), we used an uncorrected alpha level (Type 1 error rate) of 0.05 in designing our study. There are many different perspectives on adjusting for multiple comparisons in general, and randomized trials in particular. A number of researchers believe that with a primary outcome and all other outcomes treated as secondary (i.e., exploratory) there is no need for multiple comparisons.

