We will assess residuals in the longitudinal linear random effects model with normal QQ plots and estimation of the skewness and kurtosis coefficients. If these are coefficients exceed their classical cut-offs of 3 and the QQ plots confirm skewness and/or kurtosis, we will then perform a longitudinal analysis based on a random effects generalized linear model with a gamma error distribution (with SAS Proc GLIMMIX) that handles skewed and kurtotic distributions. We will fit such a model with identity link function (linear mean model), such that the resulting estimates and tests are comparable to those of the normal error random effects model. We will compare the estimates and p-values. If the two approaches agree with respect to significance at the specified alpha level, then we will use the results from the linear random effects model with normal error. If they disagree we will base results on the gamma error distribution model.

Prior to each hierarchical analysis, baseline outcomes, pre-treatment assessment scores, and demographics (except gender which by definition is balanced due to be a stratification factor in the randomization) will be compared between the two treatments at the two-sided alpha = .05 level. Any significant baseline variables will be included as covariates in the hierarchical regression models. We will also perform as a sensitivity analysis based on an adjustment of the ITT models for post-randomization confounding due to differences in medication patterns between the randomized groups. Such adjustments will be based on a causal modeling approach that distinguishes between direct effects of the iCBT intervention, on the one hand, and differences in medication patterns, on the other, using randomization and its products with baseline covariates as the instrumental variables to control for unmeasured confounding due to choice of medication.

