1. Provide the precise plan how data is to be collected or acquired (repeat the same information as listed under “Data Collection” section of this form. **At the baseline assessment interview, a member of the research team (PI, Co-I, or research coordinator) will administer a comprehensive, face-to-face interview that allows for a reliable diagnosis of schizophrenia and queries subject psychosocial functioning levels, symptomatology, substance use, service usage, and check-in. At other assessments, the independent assessor will perform semi-structured interviews, collect questionnaire data, administer cognitive and performance tests, and complete the check-in. The Supported Employment Specialists will complete the check-ins after treatment groups begin, which are not tied to an assessment (i.e., at 3-months, 9-months, and 15-months). They will collect data from the WBI at baseline, and at 6-months, 12-months, and 18-months after treatment groups begin (obtained in the course of standard SE care).**

Some data (e.g., demographics, diagnosis, study enrollment and tracking) will be stored on the centralized VA server and uploaded daily (i.e., \\VHAPHIFPCMIRECC \\Research Studies\\[name] -Integrated CBT to Improve Work). Research data from the questionnaires and some study scales (e.g., SAPS, BSES-SF) will be collected electronically via web interface, a password protected website run within the CMCVAMC firewall and stored on the VHAPHIFOCMIRECC direct-entry data server. The server is maintained by CMCVAMC FITS. Interview data and self-report data are entered directly onto computers at the research site, by research technicians and study subjects respectively. The technician will be present with the subject through the entire

assessment, and will review each instrument as it is completed. CNB data are uploaded automatically to the VA MIRECC secure server using PGP encryption and reviewed for validity (i.e., \\VHAPHIFPCMIRECC \\Research Studies\\[name] -Integrated CBT to Improve Work).

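### For WBI, scored 0 when a participant is not working, the gamma fallback cannot be fitted by full likelihood to all randomised participants, yet it decides the result if triggered

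*Combined protocol and SAP*

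**What the plan says.** Section W.4.2 (i) fits linear mixed models to continuous outcomes, with "separate main effects for change from baseline to each follow-up visit at 6, 12, and 18 months", a treatment effect and visit-by-treatment interactions. ITT contrasts at 6, 12 and 18 months come from those interactions, and WBI is named among the outcomes.

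Residuals are then checked. If the skewness and kurtosis coefficients "exceed their classical cut-offs of 3 and the QQ plots confirm skewness and/or kurtosis", the plan fits a "random effects generalized linear model with a gamma error distribution (with SAS Proc GLIMMIX) that handles skewed and kurtotic distributions" with identity link. If both models agree on significance, the normal model is reported. Otherwise: "If they disagree we will base results on the gamma error distribution model".

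The WBI entry in section O.2.1 assigns the value 0 "at points in which the participants are not working". It treats missing data separately: "WBI data may be missing if research participants refuse to allow the SE specialist to observe at the worksite". Section Y.1 gives the schedule: "They will collect data from the WBI at baseline, and at 6-months, 12-months, and 18-months after treatment groups begin".

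Section W.4.1 gives the status of WBI: "and secondary outcome, Work Behavior Inventory (WBI), we used an uncorrected alpha level". Section W.4.2 (ii) names the composite work index as primary, but then cites the WBI difference as support for Primary Aim 1. Parts (ii) and (iii) also use WBI for Secondary Aims 1 to 3.

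**The concern.** The zeros are outcome values, so the missing-data provisions in section W.4.2 (i) do not reach them. The gamma distribution lives on values above 0. The plan therefore gives the deciding vote on WBI to a model whose likelihood cannot take the score of anyone out of work, and it does not say what the gamma analysis should do with those rows.

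The likely improvisations are unattractive. Working is one of the things iCBT is meant to change, so an analysis of positive scores alone compares workers with workers and loses the protection of randomisation. If no fit is obtained at all, the plan names no deciding result. The trigger is also most likely to be met when few people work, which is when zeros are most frequent.

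**Working it through.** The plan states no figure to reproduce. The check concerns the support of the model and when the fallback would be called.

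**1. Gamma likelihood at 0.** The density is proportional to y^(k-1)·exp(-y/θ), with shape k. At y = 0 the log-density is +∞ for k < 1, finite only at k = 1 exactly, and -∞ for k > 1. In one simulated set of 96 (48 per arm, section M.3.1; assumed 30% vs 45% working), 61 values were 0. The all-participant log-likelihood was +∞ at shapes 0.5 and 0.99, and -∞ at 1.01, 2 and 5. It was finite across shapes only after the zeros were removed, leaving 12 and 23 participants.

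**2. If zeros are excluded.** Assume workers average 120 in both arms, with 30% vs 45% working:
- all randomised: 0.45×120 - 0.30×120 = 18 points;
- workers only: 120 - 120 = 0.

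A simulation of 4,000 trials gave 18.06 and -0.07. The two analyses answer different questions.

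**3. If zeros are kept under a quasi-likelihood** (variance proportional to the squared mean). An all-zero visit-by-arm cell has fitted mean 0 and variance 0. If a share p works at baseline, independently, with 48 scores per arm, the chance that at least one arm is all zero at baseline is 1 - [1 - (1-p)^48]²:

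| p | chance |
|---|---|
| 0% | 100% |
| 1% | 85% |
| 2% | 61% |
| 5% | 16% |
| 10% | 1.3% |

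The same event would make a positive-rows-only interaction inestimable. These are chances of an empty baseline cell. They are not chances that the trial's WBI result goes wrong.

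**4. When the trigger fires.** Let a share q score Normal(m, s) and the rest 0. The raw moments are qm, q(m²+s²), q(m³+3ms²) and q(m⁴+6m²s²+3s⁴), from which skewness and kurtosis follow. Assume m = 120, s = 20 and equal arms. Adding all-zero baseline rows, with even dropout to 20%, makes follow-up rows a fraction w = 2.6/3.6 = 0.72 of the total. Skewness is then divided by √w and kurtosis by w. Raw kurtosis is at least skewness² + 1, so skewness above 3 implies raw kurtosis above 10, and requiring both coefficients reduces to skewness above 3.

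| Reading of the trigger | Fires below, follow-up rows only | Fires below, with all-zero baseline |
|---|---|---|
| Both coefficients > 3 | 9% working | 12% |
| Either, excess kurtosis | 14% | 18% |
| Either, raw kurtosis | 24% | 30% |

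With s = 25 the first and last follow-up-only limits are about 9% and 25%.

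**5. Trigger and disagreement together.** This was simulated with 300 trials per scenario, 5% working at baseline, 20% dropout and a gamma fit to positive rows. If both coefficients are required, the two events coincide in 3-5% of trials at 5% vs 15% working, and in 0% from 10% vs 30% upward. With either coefficient and excess kurtosis, the figure is at most 23% at 10% vs 30%, falling to 0-1% from 20% vs 40%. The visual QQ check was taken as always confirming, so these are upper bounds.

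**6. The normal model with zeros kept.** Under no effect it rejected in 4.5%, 5.8% and 4.0% of trials at 10%, 20% and 30% working (400 trials each, Monte Carlo SE about 1.1 points).

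**The case against.** The plan is not silent on zeros. Section O.2.1 makes 0 the recorded value and section W.4.2 (i) requires ITT contrasts, which together point to keeping every row. Dropping non-workers would be a departure from the plan. This stands, and it limits what can be claimed: the workers-only figures show what to avoid, not what the plan prescribes.

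A quasi-likelihood fit could keep the zeros, and the plan names a software procedure but no estimation method. How that procedure treats zero responses is not in the documents. In a simplified check (baseline plus one follow-up, independent rows, no random effects), such a fit existed in 80-85% of trials at 5% working at baseline and 99% at 10%, and its interaction equalled the normal-model difference. Its test, however, rejected in 0-1% of trials with an effect, against 19-58% for the normal model. On that route the cost is power rather than bias, and the disagreement rule would still hand the decision to the weaker test. The text also specifies a gamma error distribution, not just a variance function.

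The trigger may never fire. The plural wording most naturally requires both coefficients, which needs very low employment. The raw-kurtosis reading is the least plausible, because a normal distribution has raw kurtosis 3: it fired in 46% of exactly normal samples of 346 residuals. This also stands.

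A reader might infer that an employment gain would be hidden or its sign reversed. The documents do not support that. The primary indices measure job attainment and weeks worked directly, and reversal needs both deleted zeros and an invented score gap between workers.

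**Conclusion.** The point holds in conditional form. For WBI, a stated decision rule rests on a model that cannot be fitted by full likelihood to all randomised participants. That follows from sections O.2.1 and W.4.2 (i) alone and needs no assumption about employment. How often it would matter does rest on assumptions: worker scores around 120 with SD 20-25, the share working, and the reading of the trigger. On the natural reading it matters only at about 9-12% working or less. On the broadest reading it could matter up to about 25-30%.

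Two stronger inferences should be resisted. The plan does not say that non-workers are removed from the WBI analysis. Nor is the primary analysis shown to be invalid: the composite is touched only if its formula, which is not given, can yield 0 or negative values. WBI is a secondary outcome. Its citation under Primary Aim 1 is a separate inconsistency, which makes a clean WBI rule more useful but does not make this a flaw in the primary endpoint.

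**What to change.** Amend section W.4.2 (i) to say three things:

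- The gamma fallback does not apply to WBI, nor to the composite if its formula can give 0 or negative values.
- No record is excluded because its value is 0.
- The linear mixed model on all rows remains the deciding ITT analysis.

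As a sensitivity check, add robust standard errors with a named small-sample correction, or a gender-stratified permutation p-value. The correction must be named: with only an n/(n-1) factor, the robust test rejected 5.0%, 7.2% and 5.0% under no effect at 10%, 20% and 30% working. The better corrections and the permutation test have not been evaluated here, and a permutation p-value alone does not supply the 95% intervals the plan requires, so neither should replace the main model. A two-part model (any work; score if working) may be added as supportive.

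The cost is one paragraph, minor programming and possibly a small loss of efficiency against a correctly specified parametric model. Sample size is unchanged. The change should be made before outcome data are seen by arm.
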